The diagnosis of AKI is based on the following criteria introduced by the Kidney Disease: Improving Global Outcomes (KDIGO) AKI Work Group in 2012 [KDIGO 2012]: increase in serum creatinine  $\geq 0.3$  mg/dL within 48 hours; or increase in serum creatinine  $\geq 1.5$  times baseline, which is known or presumed to have occurred within the prior 7 days; or urine volume < 0.5 mL/kg/hour for 6 hours. The management of AKI is purely symptomatic, with the aim of limiting damage and preventing further loss of function. No pharmacologic therapy is approved for the treatment or prevention of AKI.

It has long been recognized that after an initial ischemic or toxic injury, the kidney develops marked resistance to subsequent damage [Honda 1987, Zager 1984, Zager 1995a, Zager 1995b, Zager 1995c]. This phenomenon, which is mediated in part by an upregulation of renal cytoprotective and anti-inflammatory stress proteins (e.g., heme oxygenase 1 [HO-1], ferritin, haptoglobin, hemopexin, alpha 1 antitrypsin, interleukin 10 [IL-10]), has been referred to as "ischemic preconditioning" or "acquired cytoresistance." This phenomenon could be used in a clinical setting to preemptively protect organs, especially when a known insult is approaching.

Protocol Number: REN-003 (Original)

Date: 25 March 2019

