7 STATISTICAL METHODS OF ANALYSIS

7.1 General Principles

The statistical analyses will be reported using summary tables, listings, and figures (TLFs). All analyses and tabulations will be performed using SAS® Version 9.4 or later. Continuous variables will be summarized using descriptive statistics (sample size [n], mean, standard deviation [SD], minimum, median, and maximum). Categorical variables will be tabulated with number and percentage of subjects. Unless otherwise noted, percentages will be based on the number of subjects from the population, as appropriate.

Individual subject data will be provided in listings. All listings will be sorted by dose group (1 = 9mg SnPP, 2 = 27mg SnPP, 3 = 90mg SnPP), stratum (CKD Stage 3 patients and CKD Stage 4 patients versus healthy volunteer subjects), and collection date and time, where applicable,

Unless otherwise noted, tabulations of categorical data will present only those categories appearing in the data.

7.1.1 *Handling Missing Values*

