0 0 0 0 0 0 0 0 0 1 / CL;
RUN;
ODS OUTPUT CLOSE;
```

Note: Depending on the convergence status in the computation, Toeplitz (toep), 1st order autoregressive AR(1), and compound symmetry (CV) variance-covariance matrix will be applied sequentially. The final analysis will be based on the first matrix leading to the convergence in the computation.

7.6.2 *Absolute Change*

In addition to the percent changes from baseline, absolute change from baseline will also be analyzed using MMRM. The method of analysis will be identical after replacing variable “resp” with “T-B” in [Section 7.6.1](#).

7.6.3 *Responder Analysis*

Repeated measures responder analyses will be fitted using the generalized estimating equations (GEE) with PROC GENMOD in SAS for the proportion of patients reporting a response (defined as a 50% or greater reduction in each response biomarker from baseline) at each Visit.

The model set up is similar to MMRM ([Section 7.6.1](#)). A logit link function will be used for this binary response variable. The unstructured within-subject variance-covariance matrix will be assumed. If computational convergence is an issue, other types of variance-covariance matrices will be explored. Odds ratios and 95% confidence intervals will be presented comparing proportion of responders between dose levels at each assessment timepoint. Results will be presented for the pooled population, as well as for the CKD and healthy populations separately.

Sample SAS code is given below. Variable “resp” is coded as 1 = Responder and 0 = Non-Responder.

```
ODS OUTPUT LSMEANS=lsm DIFFS=diff ESTIMATE=estm;
PROC GENMOD DATA=dataset;
  BY ckd;
  CLASS visit dose usubjid;
  MODEL resp(EVENT='1') = base visit dose dose*visit / LINK=LOGIT DIST=BIN;
  REPEATED SUBJECT = usubjid /TYPE=UN;
  LSMEANS dose / DIFF CL;
RUN;
ODS OUTPUT CLOSE;
```

7.6.4 *Exploratory analysis*

Percent change and change in each response biomarker will be analyzed using the Cochran-Mantel-Haensel (CMH) test stratified by baseline. In the stratification, baseline will be divided into quintiles based on the pooled CKD and Healthy subjects in the MITT population. Between group comparison will be carried out at each time point using the CMH test for row mean score difference (RMS) with the modified ridit scores. Analysis will compare the 90 mg group to the 27 mg group at each timepoint overall and for CKD patients and healthy volunteers separately.

Sample SAS code is as follows:

```
PROC FREQ;
  BY visit;

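### SAP 7.6.3 promises a dose odds ratio with a 95% CI at every visit but has no rule for cells with 0% or 100% responders; its only fallback, a different working covariance, cannot repair them

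*SAP*

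**What the plan says.** SAP 7.6.3 defines a responder, separately for each biomarker and visit, as follows: "defined as a 50% or greater reduction in each response biomarker from baseline". It fits a GEE in PROC GENMOD with an unstructured working covariance and this model: "MODEL resp(EVENT='1') = base visit dose dose*visit / LINK=LOGIT DIST=BIN". There are ten post-dose visits (SAP 7.6.1).

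The promised output is: "Odds ratios and 95% confidence intervals will be presented comparing proportion of responders between dose levels at each assessment timepoint". On populations: "Results will be presented for the pooled population, as well as for the CKD and healthy populations separately".

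The only contingency in 7.6.3 is: "If computational convergence is an issue, other types of variance-covariance matrices will be explored". The MMRM section, to which 7.6.3 likens its set-up, gives an ordered list: "Toeplitz (toep), 1st order autoregressive AR(1), and compound symmetry (CV) variance-covariance matrix will be applied sequentially".

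SAP 7.1 sets the display convention: "Categorical variables will be tabulated with number and percentage of subjects". Nothing in the SAP deals with cells that contain no responders or only responders. There is no penalised or exact method, minimum count, collapsing rule or not-estimable convention. The CMH analysis in SAP 7.6.4 covers change and percent change, not responder status. Protocol 11.3 says a responder analysis will be considered and leaves its definition and method to the SAP.

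**The concern.** With dose-by-visit in the model, every dose-visit cell has its own free log-odds. When all subjects in a cell have the same outcome, that log-odds runs to plus or minus infinity. Any odds ratio against the cell is then zero, infinite or undefined. This is separation in the mean model, and the working covariance is a different part of the model.

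The fallback is also triggered by the wrong signal. It is invoked on non-convergence, but a fit with an empty cell can report convergence at an arbitrary large log-odds with a small robust standard error. Trying matrices until one converges could therefore print a dose difference that is an artefact. Biomarker effect and choice of dose are stated objectives, so such a result could mislead.

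Separately, `LSMEANS dose` in the sample code averages over visits, so it does not give the per-timepoint odds ratios that the text promises.

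**Working it through.** **Inputs from the documents.** SAP 3 plans 6 healthy volunteers at each of 9, 27 and 90 mg. It plans 6 stage 3 and 6 stage 4 subjects at each of 27 and 90 mg. The total reproduces: 3×6 + 2×6 + 2×6 = 42. Subjects per cell are therefore:
- healthy: 6, 6, 6
- CKD (stages combined, no 9 mg group): 12, 12
- pooled: 6 at 9 mg, 18 at 27 mg, 18 at 90 mg

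**Assumptions.** No document gives a responder rate p, so I use 5, 10, 20, 30 and 50%. The rate is equal in the two groups compared, and all subjects are evaluable.

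**Formulas.** The chance that a cell is all-or-none is q(n) = (1−p)^n + p^n. The chance that a single-visit odds ratio is non-finite is 1 − [1 − q(n1)][1 − q(n2)].

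Example at p = 20%, 6 v 6: q(6) = 0.8^6 + 0.2^6 = 0.262, and 1 − 0.738² = 0.456.

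| Comparison | 5% | 10% | 20% | 30% | 50% |
|---|---|---|---|---|---|
| Healthy, any pair (6 v 6) | 93% | 78% | 46% | 22% | 6% |
| Pooled, 9 mg v a higher dose (6 v 18) | 84% | 60% | 28% | 12% | 3% |
| CKD, 90 v 27 mg (12 v 12) | 79% | 49% | 13% | 3% | 0.1% |
| Pooled, 90 v 27 mg (18 v 18) | 64% | 28% | 4% | 0.3% | 0% |

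**Expected number of non-finite odds ratios per blood biomarker.** These expectations do not depend on the within-subject correlation.
- All dose pairs: 30 healthy + 10 CKD + 30 pooled = 70 odds ratios. At 20% the expected count is 30(0.456) + 10(0.133) + 10(0.036) + 20(0.276) ≈ 21. Across the five rates it is 59/43/21/9/2.5.
- 90 v 27 mg only: 3 populations × 10 visits = 30 odds ratios. At 20% it is 10(0.456 + 0.133 + 0.036) ≈ 6.2. It is 2.5 at 30% and 0.6 at 50%.

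**Unequal rates.** With 10% in one group of six and 50% in the other, the chance is 1 − (1 − 0.531)(1 − 0.031) ≈ 55%. A real dose effect does not remove the problem.

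**Why the fallback cannot work.** With complete data and no covariate, the saturated dose-by-visit GEE reproduces the observed cell proportions whatever the working correlation. An observed 0/6 therefore stays at zero. With baseline added, I rely on simulation (statsmodels, not SAS): 60 healthy-volunteer trials, no dose effect, 20% rate, latent correlation 0.6. An all-or-none cell occurred in 59 of the 60. In those 59:
- independence reported convergence in 59 and exchangeable in 5;
- where exactly one of the two compared cells was all-or-none, the 95% CI excluded 1 in 754 of 754 comparisons (independence) and 76 of 76 (exchangeable).

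In a separate set of 300 null trials across the five rates, the unstructured matrix failed in all 300, including 39 with no all-or-none cell. That failure is not due to empty cells alone, but it would bring the fallback into play.

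**The case against.** **Low stakes.** Percent change is the efficacy endpoint in SAP 7.6.1, the responder analysis is secondary to it, and escalation rests on safety, tolerability and PK. The MMRM and CMH analyses use the same biomarkers without this failure. This stands and limits the severity.

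**Frequency is undocumented.** This also stands. A reader might infer that most responder odds ratios will be undefined, because a response is a fall while Protocol 6.1 describes a phenomenon "mediated in part by an upregulation of renal cytoprotective and anti-inflammatory stress proteins (e.g., heme oxygenase 1 [HO-1], ferritin, haptoglobin, hemopexin" among others. The documents do not support that inference. The passage concerns renal proteins after injury, not blood levels after SnPP. It does not mention bilirubin or P21. Protocol 6.2 calls SnPP a heme oxygenase inhibitor, so falls in some markers are plausible. Low rates cannot be ruled out, and that is all that can be said.

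**The count of 70 is the widest reading.** The ESTIMATE statements in 7.6.1 and the CMH comparison in 7.6.4 single out 90 v 27 mg, which gives 30. However, 7.6.3 speaks of dose levels generally and its `DIFF` option produces all pairs, so both counts are shown.

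**The software evidence is indirect.** A reader might infer that GENMOD will print false dose differences. That was not run, and its messages and output may differ. The infinite log-odds does not depend on software.

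**The code is only a sample.** Table specifications are in a separate document (SAP 11) and could hold a display rule. Even so, the SAP text itself supplies neither the rule nor code that gives what it promises.

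**Replacing the GEE with per-visit Firth models would be a preference.** This stands. With no responders in any group (n = 18, baseline adjusted), the Firth 90 v 9 mg odds ratio ranged from 0.62 to 1.49 (central 95% over 500 random baselines). It is a non-null figure from zero events.

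**Conclusion.** The point holds as a missing rule in a supportive analysis and should be corrected. As written, 7.6.3 promises estimates that do not exist whenever a compared cell is all-or-none, and its fallback addresses a different fault. The exposure is greatest for healthy volunteers (46% per odds ratio at a 20% rate, 6% at 50%). It is milder in CKD (13% and 0.1%). Per blood biomarker, about 21 of 70 odds ratios are non-finite at 20% and 2.5 at 50% if all pairs are compared, or about 6 and 0.6 of 30 for 90 v 27 mg alone. These figures rest on assumed equal rates and complete data. The spuriously narrow interval is an illustrated risk, not a demonstrated GENMOD result. The mismatch between `LSMEANS dose` and the promised per-visit output can be read directly from the SAP. Nothing here shows that the MMRM results or dose escalation would be affected, or that the GEE has to be abandoned.

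**What to change.** Amend SAP 7.6.3 as follows.

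1. Report responders as n/N with exact Clopper-Pearson 95% CIs by dose, population and visit. Counts and percentages already follow from SAP 7.1.
2. Replace `LSMEANS dose` with per-visit dose contrasts from the dose-by-visit term, exponentiated to odds ratios. State that no GEE odds ratio or CI is reported when either cell is 0% or 100%, whether or not the fit reports convergence.
3. Optionally, for those suppressed comparisons, give a per-visit Firth-penalised odds ratio with a profile-likelihood 95% CI, labelled supportive. Show n/N only when both cells are all non-responders or both are all responders.

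The cost is SAP wording and short code, with no new data. The downside is that some promised odds ratios will appear as not estimable, and intervals at n = 6 will be very wide. For 0/6 the Clopper-Pearson interval is 0 to 46% (upper limit 1 − 0.025^(1/6) = 0.459). For 0/6 v 1/6 the unadjusted Firth odds ratio is (1.5/5.5)/(0.5/6.5) = 3.5, with a profile 95% CI of about 0.15 to 562.

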3 STUDY OVERVIEW

This is a Phase 1b, single-center, dose-escalating study to evaluate the safety, tolerability, PK and pharmacodynamic effect of SnPP in healthy volunteers and in subjects with stage 3-4 CKD. The following biomarkers will be used as surrogate measures of cytoprotective activity: Haptoglobin, Ferritin, Bilirubin, Hemopexin, IL-10, and Heme Oxygenase-1. Additionally, the P21 biomarker will be monitored at various points of the study as well as urine biomarker response to SnPP.

Subjects who meet all inclusion criteria and none of the exclusion criteria are eligible to be enrolled into the study.

The study is designed as follows:

- A screening period with baseline evaluations for study eligibility.
- If subjects meet eligibility criteria, they will receive SnPP by slow intravenous injection over a 120-minutes on study day 1.
- Subjects will stay in the clinic for the initial 24 hours after administration of SnPP and will be discharged at the end of study day 2 if no safety issues appear.
- The study will initially be dose-escalating in 3 groups of 6 healthy volunteers each, for a total of 18 healthy volunteers, evaluating escalating single dose of SnPP starting with a dose of 9 mg SnPP, followed by 27 mg SnPP, and 90 mg SnPP. Dose-escalation from one dose level to the next will only be allowed after a careful review of the safety, tolerability and PK data from the prior dose group as determined by the Data and Safety Monitoring Board (DSMB).
- After a careful review of the safety, tolerability and PK data from all dose groups from the healthy volunteer cohorts, the Data and Safety Monitoring Board (DSMB) will determine whether to proceed to the CKD cohorts. If the determination by the DSMB allows to proceed to the CKD cohorts, subjects with stage 3 CKD will be in 2 groups of 6 each, for a total of 12 subjects, evaluating escalating single dose of SnPP starting with a dose of 27 mg SnPP followed by 90 mg SnPP. Dose-escalation from one dose level to the next will only be allowed after a careful review of the safety, tolerability and PK data from the prior dose group as determined by the Data and Safety Monitoring Board (DSMB).

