- After a careful review of the safety, tolerability and PK data from all dose groups from the stage 3 CKD cohorts, the Data and Safety Monitoring Board (DSMB) will determine whether to proceed to the stage 4 CKD cohorts. If the determination by the DSMB allows to proceed to the stage 4 CKD cohorts, subjects with stage 4 CKD will be in 2 groups of 6 each, for a total of 12 subjects, evaluating escalating single dose of SnPP starting with a dose of 27 mg SnPP followed by 90 mg SnPP. Dose-escalation from one dose level to the next will only be allowed after a careful review of the safety, tolerability and PK data from the prior dose group as determined by the Data and Safety Monitoring Board (DSMB).
- Subjects will be followed for 28 days after the dose of SnPP. Response biomarkers will be assessed at baseline and 2, 4, 8, 12, 18, 24, 48, 72, 96 and 168 hours after study drug administration. Safety will be assessed for up to 28 days after study drug administration.
- Blood samples for SnPP pharmacokinetic analysis will be assessed at baseline and 1, 2, 3, 4, 6, 8, 12, 18, and 24 hours after study drug administration. These data will be used in the dose escalation decision making review process along with the safety and tolerability of the previous dose. Urine samples will be collected and centrifuged and analyzed for subject responsiveness to SnPP therapy.
- Urinary Clearance of SnPP will be assessed by the measurement of tin in a 24-hour urine sample.

- Total study duration will be 29 days for each subject, in addition to a screening period of up to 14 days. Up to a total of 42 subjects consisting of 18 healthy volunteers and 24 chronic kidney disease (stage 3-4) subjects will receive single escalating doses of SnPP.

For a complete list of assessments performed throughout the study, see Time and Events Schedule ([Section 10](#)).

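### Five baseline strata are too many for the exploratory rank test of 90 mg against 27 mg in 6 v 6 healthy volunteers

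*SAP*

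**What the plan says.** SAP section 7.6.4 analyses percent change and absolute change in each response biomarker with a stratified rank test, "using the CMH test for row mean score difference (RMS) with the modified ridit scores". On the strata it says: "In the stratification, baseline will be divided into quintiles based on the pooled CKD and Healthy subjects in the MITT population". On the comparisons it says: "Analysis will compare the 90 mg group to the 27 mg group at each timepoint overall and for CKD patients and healthy volunteers separately". There is no rule for sparse strata or for strata that contain only one dose.

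The group sizes come from SAP section 3:
- Healthy volunteers: "3 groups of 6 healthy volunteers each, for a total of 18 healthy volunteers", at doses "starting with a dose of 9 mg SnPP, followed by 27 mg SnPP, and 90 mg SnPP". Six subjects at 27 mg and six at 90 mg enter this contrast.
- CKD stage 3: "subjects with stage 3 CKD will be in 2 groups of 6 each, for a total of 12 subjects".
- CKD stage 4: "subjects with stage 4 CKD will be in 2 groups of 6 each, for a total of 12 subjects".

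Both CKD stages are dosed at 27 mg and 90 mg only, so the CKD contrast is 12 v 12 and the overall contrast is 18 v 18. Protocol section 11.3 and the SAP both label the test exploratory. SAP section 8 states that there was no formal sample size calculation.

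**The concern.** A stratified rank test compares doses only within a stratum. Twelve healthy volunteers over five strata average 12/5 = 2.4 subjects each. Some strata will hold only 27 mg or only 90 mg subjects, and these drop out of the statistic. In a stratum of two or three, a rank says little more than which value is larger.

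This is the plan's only rank-based dose comparison. The other analyses of the continuous changes are repeated-measures models on untransformed values. A non-significant healthy-volunteer result could therefore reflect the stratification rather than the absence of a dose effect.

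**Working it through.** The plan states no power or information figure for this test, so there is nothing of its own to reproduce. The head count agrees: 3×6 + 2×6 + 2×6 = 42 subjects.

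**Inputs.** Healthy volunteers 6 v 6, CKD 12 v 12, overall 18 v 18 (SAP section 3). Five strata are cut on all 42 subjects, giving stratum sizes 8, 9, 8, 9, 8. Assumptions: all 42 are in the MITT population, and dose is unrelated to baseline unless stated.

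**Linear measure.** Information is the sum over strata of n27·n90/(n27+n90). Unstratified, 6 v 6 gives 6×6/12 = 3. With N subjects in K non-empty strata, the expected share kept is (N − K)/(N − 1).
- Healthy volunteers with baselines distributed as in CKD: expected K = 4.79, share kept (12 − 4.79)/11 = 0.66, loss 34%. The 5th to 95th percentile of the loss is 6% to 67%.
- About 3.32 of 12 subjects (3.32/12 = 28%) fall in one-dose strata.
- CKD: (24 − 5)/23 = 0.83, loss 17%. Overall: (36 − 5)/35 = 0.89, loss 11%.

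**Rank-test measure.** Modified ridit scores weight each stratum by n27·n90/(n+1), where n is the stratum size. Unstratified, this is 36/13. With like baselines, the expected loss is 46% for healthy volunteers, 28% for CKD and 20% overall.

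**Sensitivity to the baseline gap between healthy volunteers and CKD (loss in the 6 v 6 comparison).**

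| Gap between populations | Linear, equal SD | Linear, HV SD halved | Rank, equal SD | Rank, HV SD halved |
|---|---|---|---|---|
| 0 | 34% | 32% | 46% | 43% |
| 1 SD | 30-31% | 25% | 41% | 35% |
| 2 SD | 22% | 18% | 31% | 26% |
| 3 SD | 17% | 16% | 25% | 23% |

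**Which feature causes the loss?** Quintiles cut on the 12 healthy volunteers alone give strata of 2, 3, 2, 3, 2. The linear share kept is (12 − 5)/11 = 0.64, a loss of 36%, and the rank-measure loss is 51%. Both are slightly worse than pooled cuts. Three strata of four lose 18% and 29%. A median split loses 9% and 16%. The loss follows the number of strata.

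**Power, healthy volunteers 6 v 6.** Simulated with normal data, an assumed 1.5 SD effect, two-sided 5%, balanced cohorts, and healthy-volunteer and CKD baselines alike. Separate runs differ by about one percentage point.

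| Correlation of baseline and response | Planned quintiles | Median split | Unstratified | Rank ANCOVA |
|---|---|---|---|---|
| 0 | 30% | 56% | 58% | 54% |
| 0.4 | 35% | 59% | 58% | 61% |
| 0.7 | 47% | 70% | 58% | 75% |

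With a 2 SD gap between populations the planned test reaches 42-56%, against 55-75% for the median split and rank ANCOVA.

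**False positives with no drug effect.** These assume a 1 SD baseline imbalance between the 27 mg and 90 mg cohorts. At correlation 0.7 the unstratified test rejects in 17% of trials. The median split rejects in about 7-10% (correlation 0.7 to 0.9) and the planned quintiles in about 3-4%. Rank ANCOVA stays at or below 5%.

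**The case against.** The strongest reply is that the stratification serves a purpose. The dose groups are sequential cohorts opened after board review, with no randomisation described, so baseline differences between 27 mg and 90 mg can confound the comparison. Percent change is computed as 100×(T − B)/B (SAP section 7.6.1), which ties it to baseline by construction. The quintiles do control this: about 3-4% false positives against 17% without strata under the imbalance above. With a strongly prognostic baseline (correlation 0.9) and balanced cohorts they even slightly beat the unstratified test on power, 63% v 59%. This stands. A reader might infer that the strata bring no gain, and the documents do not support that. It is a reason to keep baseline adjustment, but not to make it with five strata.

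The second reply is that little rests on this test. It also stands: escalation is decided on safety, tolerability and PK, and the repeated-measures model with baseline as a covariate already analyses healthy volunteers separately. A reader might infer that the rank test is the plan's only protection against skewed biomarkers. SAP section 7.6.3 also has a responder analysis on a 50% threshold, reported for healthy volunteers, and medians and ranges are tabulated.

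A reader might also blame the pooled cut points. The check points the other way. Cuts made on healthy volunteers alone lose slightly more, and when the two populations differ, pooled cuts leave the volunteers in fewer strata and lose less.

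**Conclusion.** The point holds as a minor one. Five baseline strata are too many for the 6 v 6 healthy-volunteer comparison. The expected loss is roughly 16-34% on the linear measure and 23-46% on the rank-test measure, with up to about 28% of subjects in one-dose strata. CKD and overall lose less, about 17% and 11% on the linear measure.

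It is tempting to say flatly that a third of the information is discarded. That figure is an expectation on the linear measure when healthy and CKD baselines are alike. The documents contain no baseline data to confirm it, and it is not the measure that matches the specified test. The losses count only sparse strata and give no credit for baseline adjustment. The power figures do give that credit, and rank ANCOVA still exceeds the planned test in every scenario tried. Effect size, correlations and imbalance are all assumed.

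**What to change.** In SAP section 7.6.4, replace quintile stratification with rank ANCOVA. Rank the response and the baseline, regress one on the other, and apply the mean-score test to the residuals. Do this within healthy volunteers and within CKD, and stratify by population in the overall comparison. Protocol section 11.3 already allows stratification by diagnosis.

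A median split computed within the population analysed is a weaker fallback: it recovers most of the power but leaves some residual baseline confounding. Dropping adjustment altogether is not advised, for the same reason.

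The sample code should be rewritten in the same edit. It puts the baseline variable itself in the table request, with no visible quintile variable and no CMH option. If that variable held raw values, nearly every subject would be a separate stratum.

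The cost is a few sentences and a few lines of code in an exploratory analysis, with no change to data collection. If baseline were unrelated to response, rank ANCOVA would give up a little power against an unstratified test (54% v 58% above).

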7.6 Efficacy Analysis

7.6.1 *Percent Change in Response Biomarkers*

The efficacy endpoint is the percent change (PCH_T) in each response biomarker relative to the Baseline period.

PCH_T will be calculated as $100 \times (T - B)/B$, where T and B are Response biomarker at 2, 4, 8, 12, 18, 24, 48, 72, 96 and 168 hours post dose (T) and baseline period (B).

PCH_T will be analyzed using a Mixed-Effect Model for Repeated Measure (MMRM) as follows:

- A 2-way MMRM pooling stage 3 and stage 4 CKD patients and healthy subjects together
- A 2-way MMRM pooling stage 3 and stage 4 CKD patients together
- A 2-way MMRM for Healthy subjects

The model will include dose level, visit (2, 4, 8, 12, 18, 24, 48, 72, 96 and 168 hours), and dose-by-visit interaction as factors and baseline response biomarker as covariate. The model parameters will be estimated using the restricted maximum likelihood method with the toeplitz variance-covariance matrix and Kenward-Roger estimate for the denominator degrees of freedom. The between dose comparison will be performed using contrast in the main effect and the simple contrast at each time point. Least squares mean (LSM) and the associated 95% confidence interval (CI) for each dose level will be presented. The difference in LSM between doses and the 95% CI for the difference will also be presented. Results will be presented for the pooled population, as well as for the CKD and healthy populations separately.

Additionally, LSM for each dose group will be plotted over time for the CKD patients and healthy volunteers pooled population as well as for each population separately. Dose response relationship will be examined graphically and may be analyzed where appropriate.

A sample SAS code is provided as follows. The code assumes that “visit” has 10 values (2, 4, 8, 12, 18, 24, 48, 72, 96 and 168 hours), “dose” is coded as 1 = 9 mg SnPP, 2 = 27 mg SnPP, and 3 = 90 mg SnPP, “ckd” is coded as 2= CKD patients and healthy volunteers pooled, 1 = patients with CKD, 0 = healthy volunteers, and “resp” = PCH_T, the % change from baseline being analyzed.

```
ODS OUTPUT LSMEANS=lsm DIFFS=diff ESTIMATE=estm;
PROC MIXED DATA=XXXX;
BY ckd;
CLASS dose usubjid visit;
MODEL resp = base visit dose dose*visit / DDF=KR;
REPEATED visit / SUBJECT=usubjid(dose) TYPE=UN;
ESTIMATE "90 mg v 27 mg overall" dose 1 0 -1;
LSMEANS dose / DIFF CL;
ESTIMATE "90 mg v 27 mg @ 168 hours " dose 0 -1 1
dose*visit 0 0 0 0 0 0 0 0 0 0
0 0 0 0 0 0 0 0 0 -1

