  TABLE base*dose*resp / SCORE=MODRIDIT;
RUN;
```

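### The sample code in SAP 7.6.3 and 7.6.4 does not deliver the visit-specific responder odds ratios or the 90 v 27 mg CMH test that the text specifies (minor)

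*SAP*

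**What the plan says.** **Responder analysis (SAP 7.6.3).** The text commits to this output: "Odds ratios and 95% confidence intervals will be presented comparing proportion of responders between dose levels at each assessment timepoint". The sample GENMOD model is "MODEL resp(EVENT='1') = base visit dose dose*visit / LINK=LOGIT DIST=BIN", so dose may act differently at each of the ten post-dose visits. The only statement that compares doses is "LSMEANS dose / DIFF CL". The block has no within-visit comparison, no ESTIMATE statement and no request to exponentiate.

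**CMH analysis (SAP 7.6.4).** The text asks for the row-mean-score statistic with modified ridit scores, stratified by baseline quintiles formed in the pooled MITT population. The comparison is also stated: "Analysis will compare the 90 mg group to the 27 mg group at each timepoint overall and for CKD patients and healthy volunteers separately". The sample PROC FREQ code names no input data set, is run by visit only, and has one table request: "TABLE base*dose*resp / SCORE=MODRIDIT".

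**Doses.** SAP 7.6.1 defines the dose variable, which "is coded as 1 = 9 mg SnPP, 2 = 27 mg SnPP, and 3 = 90 mg SnPP". SAP 3 gives all three doses to healthy volunteers (three groups of 6). Each CKD stage gets only 27 and 90 mg (two groups of 6 per stage).

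**The concern.** Sample code in a SAP is a natural template for the programmer. Where it departs from the text, the plan no longer fixes a single analysis.

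- **Responders.** A dose effect confined to part of the week would be diluted by averaging over ten visits, and the output would be on the log-odds scale although the text promises odds ratios.
- **CMH.** The missing CMH request is obvious and would be repaired on first use. The missing dose restriction is easier to overlook. After that repair, a p-value influenced by the 9 mg group could be reported as the 90 v 27 mg comparison.

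This has some weight because choosing a dose is a stated objective (SAP 2) and 90 v 27 mg is the only dose contrast available in CKD.

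**Working it through.** The documents give no effect size, SD or power on this point, so there is no planned figure to reproduce. The check sets code against text, then sizes the consequences under stated assumptions.

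**1. Responder output: number of estimates**

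Dose pairs: C(3,2) = 3 in the pooled and healthy sets, C(2,2) = 1 in CKD. There are ten visits.

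| Set | Odds ratios promised | Differences from the code |
|---|---|---|
| Pooled | 3 × 10 = 30 | 3 |
| Healthy | 3 × 10 = 30 | 3 |
| CKD | 1 × 10 = 10 | 1 |

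**2. Responder output: what is estimated**

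With a dose-by-visit interaction and a logit link, the least-squares mean for a dose is the average of its ten visit logits. The difference between two doses is therefore

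(1/10) × Σ log OR(visit).

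A logistic GEE fitted to simulated data confirmed this: ten visit log odds ratios from −0.43 to 0.63 averaged 0.078, and the LSMEANS-type difference was also 0.078.

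Assumed example: log OR 1.5 at three visits (OR = e^1.5 = 4.48) and 0 at seven (OR = 1). The average is 3 × 1.5 / 10 = 0.45, and e^0.45 = 1.57. The code would print 0.45.

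**3. CMH code against CMH text**

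| Text of 7.6.4 | Printed code |
|---|---|
| CMH row-mean-score test | Modified ridit scores set, but no CMH option: crosstabulations only |
| 90 v 27 mg | No restriction on a three-level dose variable |
| Overall, CKD and healthy | By visit only, although the code in 7.6.1 and 7.6.3 has a BY ckd statement |
| Baseline quintile strata | Stratum called base, the name of the baseline covariate in 7.6.1; no derivation shown |

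If base were the continuous baseline with distinct values, each stratum would hold one subject and no statistic could be computed.

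**4. If CMH were added to unfiltered data**

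Degrees of freedom are the number of doses minus 1: 2 in the healthy and pooled sets, 1 in CKD. In CKD the test is already 90 v 27 mg, and a trial run with and without the filter gave the same statistic.

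**5. Size of the effect**

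Simulation inputs: planned layout (healthy 6/6/6; CKD 12 at 27 mg and 12 at 90 mg), normal outcomes, five strata from pooled baseline quintiles, no 90 v 27 mg difference, nominal 5%. The shifts are assumptions.

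| Set and assumption | Three-dose test rejects | 90 v 27 mg test rejects |
|---|---|---|
| Healthy; 9 mg differs by 1 / 1.5 / 2 SD | about 18% / 36% / 55% | about 4% |
| Pooled; CKD and healthy outcomes differ by 1 / 2 SD, equal baselines | about 14% / 32% | about 4% / 1% |
| Pooled; same, baselines differing by 2 SD | about 6% / 9% | about 4% |

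The pooled rows contain no dose effect at all. Because every 9 mg subject is a healthy volunteer, a difference between populations looks like a dose difference. When baselines also differ, the baseline strata partly separate the populations and the excess shrinks.

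**The case against.** The strongest reply is that the text governs. Both blocks are labelled as sample code, and the text states the comparison, timepoints, populations, statistic and strata. 7.6.3 also refers to the set-up of 7.6.1, whose code has a within-visit ESTIMATE at 168 hours. The ODS line in 7.6.3 asks for ESTIMATE output although no such statement is printed, which suggests that lines were left out. The PROC FREQ block names no data set, so a dose filter, a population split or a derived quintile called base could all exist upstream. SAS prints degrees of freedom, so an unfiltered test would show 2. Table specifications are in a separate document (SAP 11), so nobody can say how a log-odds difference would be labelled. SAP 7.6.4 and Protocol 11.3 call the CMH analysis exploratory.

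Most of this stands, and it limits the severity. It does not remove the mismatch: run as printed, neither block gives the promised output.

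The reply also rules out stronger readings that a reader might infer:

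- *The CMH code tests three doses.* As printed it tests nothing. The three-dose test needs an added CMH request and unfiltered data, and even then does not arise in CKD.
- *One number replaces ten odds ratios.* That is true per dose pair, and overall only in CKD.
- *The stratum is the wrong variable.* The code leaves base undefined; it does not contradict the quintile rule.
- *Pooled false positives run at 14% to 32%.* That holds only for equal baselines in CKD and healthy subjects.

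**Conclusion.** The sample code in SAP 7.6.3 and 7.6.4 does not deliver the analyses that the text specifies. The responder code gives 3, 3 and 1 visit-averaged log-odds differences (pooled, healthy, CKD) where the text needs 30, 30 and 10 odds ratios. The PROC FREQ code is incomplete: no CMH request, no population split, no dose restriction and no demonstrated quintile.

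The mismatches follow from reading code against text and need no assumptions. The rejection rates do rest on assumptions: a CMH request added to unfiltered data, and shifts that the documents do not give. In the healthy set the error could be large; in the pooled set it ranges from slight to large, depending on how far baselines separate the populations. The severity is minor, because the intended analyses can be recovered from the text and 7.6.4 is exploratory.

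**What to change.** **7.6.3:** replace the LSMEANS line with dose comparisons within visit, exponentiated, for example `SLICE dose*visit / SLICEBY=visit DIFF CL EXP;`, and report the exponentiated estimates with their 95% CIs.

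**7.6.4:** name the input data set and use `WHERE dose IN (2,3); BY ckd visit; TABLES basequint*dose*resp / CMH2 SCORES=MODRIDIT;`. Define basequint as the baseline quintile in the pooled MITT population. The ckd coding in 7.6.1 already has values for the pooled, CKD and healthy sets.

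**Cost:** a few lines of SAP code. No change to data collection, endpoints or the analyses described in the text.
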